## 6 Study treatment

#### 6.1 Treatment procedure

Subjects who fulfill the above inclusion criteria, do not meet any of the exclusion criteria, will start receiving MTX 6 to 8 mg/week after completing assessments at Week 0. Also, 10 mg of folic acid will be orally administered once a week 48 hours after the first MTX dosing day of the week to prevent ADRs related to MTX (A daily dosage of 1 mg folic acid is acceptable in South Korea on a condition that the dosage cannot be changed during the study period).

To achieve remission, the dosage of MTX will be promptly escalated to the maximum tolerable dose (MTD)  $\leq$ 25 mg/week (the maximum dose should be set according to the package insert of each country) in line with EULAR Recommendations 2016, and will be in principle maintained at the MTD from Week 12 onward. Also, the dosage of MTX will

remain unchanged from Week 20 to 24 except for dose reduction/interruption due to an ADR. Weekly dose of MTX will be administered orally at once or twice a day in principle. If the dosage of MTX is maintained  $\geq 10$  mg/week and SDAI remission is achieved at Week

24, the MTX therapy will be continued until Week 48 (ARM-1).

If SDAI remission is not achieved despite the maintenance of  $\geq 10$  mg/week MTX dose at Week 24, ADA 40 mg will be administered subcutaneously every other week until Week 48. Subjects then will be stratified by countries (Japan, South Korea, and Taiwan) as a stratification factor, and for each stratum, subjects will be randomized at a 1:1 ratio to either a group in which the MTD of MTX (10 to 25 mg/week) will be maintained (ARM-2), and a group in which the dosage of MTX will be reduced to 6 to 8 mg/week (ARM-3).

The MTX dosage shall be either 6 mg/week or 7.5 mg/week in subjects in ARM-3 whose maintenance dose of MTX at Week 24 is 10 mg/week.

Subjects in whom MTX at a dosage  $\geq 10$  mg/week cannot be maintained at Week 24 due to ADR, etc. will be withdrawn from the study.

Subjects in whom MTX at a dosage of  $\geq 10$  mg/week in ARM-2 or  $\geq 6$  mg/week in ARM-3 cannot be maintained after Week 24 due to ADR, etc. will also be withdrawn from the study. Also, subjects will be withdrawn from the study when an increased dosage of MTX is required after Week 24 due to loss of efficacy, etc.

The dose status of MTX, folic acid, and ADA, as well as the treatment groups in Week 24 onward (ARM-1 to -3) should be recorded in EDC.

## 6.1.1 Dose selection of MTX for study treatment

This study is intended to evaluate the optimal dosage of MTX in combination with ADA by comparing between a group (ARM-2) maintaining the dosage of MTX at the maximum tolerable dose (MTD;  $\geq 10$  mg/week) and a group (ARM-3) reducing the dosage of MTX to 6 to 8 mg/week.

In ARM-2, MTX is maintained at the MTD. Not overlapping the dosage of MTX in ARM-3, the lower limit of MTD was determined to be 10 mg/week based on the results of the HAWK post-marketing surveillance study of ADA in which the mean dosage of the combined use of MTX was 12.7 mg/week, and it also showed the dosage of MTX of  $\geq$ 10 mg/week could be maintained in combination with ADA (Tanaka Y, et al. 2018: 1-9) and the results of the CONCERTO study conducted in the US and Europe, which confirmed no differences in efficacy among MTX doses of  $\geq$ 10 mg/week in combination with ADA (Burmester GR, et al. 2015:1037-44).

The dosage of MTX in ARM-3 was determined based on the results of the HOPEFUL 1 study, which confirmed that MTX is effective at doses of 6 to 8 mg/week in combination with ADA (Takeuchi T, et al. 2014: 536-43).

## 6.2 Concomitant therapies

Allowed concomitant therapy and prohibited concomitant therapy are as follows. The dosage and administration route of drugs used for treatment of RA during the study should be recorded in EDC.

## 6.2.1 Allowed concomitant therapy

Oral and suppository formulations (both  $\leq 10 \text{ mg/day}$  prednisolone equivalents) and external application (dermatologics, eye-drops, nasal drops, and inhalants) of corticosteroids and NSAIDs are allowed for concomitant use; provided that the dosages of corticosteroid oral drug and suppository should in principle remain unchanged from Week 24 to 48. Moreover, subjects are allowed to use corticosteroids via an intracapsular administration (except for 28 days before efficacy assessment), intravenous corticosteroids (10 mg/day prednisolone equivalents) temporarily prescribed because of difficulties in oral administration and other reasons, and corticosteroids temporarily prescribed for indications other than rheumatoid arthritis.

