## 9.2.1.1 Method of analysis for primary efficacy endpoint

The primary analysis for this study is intended to demonstrate the non-inferiority of ADA/MTX-Reduced Dose Group (ARM-3) to ADA/MTX-MTD Group (ARM-2) in terms of the primary endpoint, that is, SDAI remission rate at Week 48. The intergroup difference in the SDAI remission rate and its two-tailed 90% confidence interval will be calculated based on a stratified analysis with country as a factor in mFAS as the main statistical analysis set. The non-inferiority margin shall be -15%.

Moreover, a multivariate statistical analysis on the SDAI remission rate at Week 48 will be performed for the following variables; age, gender, autoantibody profile, SDAI at screening, and change in mTSS from screening to Week 24.

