#### 9.3 Significance level

The analysis on non-inferiority will be performed with a two-tailed confidence interval of 90%. A two-tailed significance level of 5% will be used for all other analyses unless specified otherwise.

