#### 9.4 Number of subjects

• Target number of subjects to be enrolled

300 subjects (target number of subjects to be enrolled in each study site is shown in the list of study sites.)

• Randomization ratio

Subjects will be stratified by countries (Japan, South Korea, and Taiwan) as a stratification factor, and for each stratum, randomized to ARM-2 and ARM-3 at the ratio of 1:1.

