## 9.4.1 Sample size selection

Assuming that the SDAI remission rate is 30% for both ARM-2 and ARM-3, and the noninferiority margin is -15%, the number of subjects required for the lower bound of a twotailed 90% confidence interval for the intergroup difference in SDAI remission rate to exceed the non-inferiority margin at 80% power of detection would be 220 subjects in total (110 in each group).

Past reports suggest that the remission rate of MTX monotherapy is about 15%. Also, it has been reported that about 10% of patients cannot continuously receive MTX  $\geq$ 10 mg/week (Atsumi T, et al. 2016: 75-83). Thus, in order to randomize 220 subjects between ARM-2 and ARM-3, 288 subjects need to be enrolled, and considering some dropouts, a sample size of 300 subjects was selected as the target number of subjects to be enrolled.

<Justification for the estimated SDAI remission rate in ADA/MTX-Reduced Dose Group (ARM-3)>

The estimated SDAI remission rate in ARM-3 was calculated in reference to the results of the MTX Monotherapy  $\rightarrow$  ADA+MTX Group in HOPEFUL 1 Study in which Japanese MTX naïve patients receiving ADA+MTX or MTX alone for 26 weeks, and then, all subjects receiving ADA+MTX for another 26 weeks (Takeuchi T, et al. 2014: 536-43). Since the maximum dosage of MTX in HOPEFUL 1 Study was 8 mg/week (6.6±0.8 mg/week: Mean±SD), the results cannot be directly extrapolated to this study in which the maximum dosage of MTX up to Week 24 will be 16 mg/week; yet, the results would be appropriate to use as a reference for the SDAI remission rate in ARM-3 in which the dosage of MTX will be reduced to 6 to 8 mg/week from Week 24 onward. ARM-3 is designed for patients who have not achieved to SDAI remission at Week 24; thus, assuming that the subjects with SDAI remission at Week 26 in HOPEFUL 1 Study (20 subjects = 163 subjects × 12%) remain to be remission at Week 52, the Week-52 SDAI remission rate among the subjects with SDAI non-remission at Week 26 was calculated to be 31.5% [45/143 subjects, that is (65 subjects - 20 subjects)/(163 subjects -20 subjects)]. Therefore, the SDAI remission rate in ARM-3 was assumed to be 30%.

<Justification for the estimated SDAI remission rate of  $\leq$ 3.3 in ARM-2 (ADA/MTX-MTD Group)>

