3.1.2. Per protocol set (PPS)

PPS is defined as a group of subjects among mFAS who adequately complied with the protocol after excluding subjects with the following significant protocol deviations, e.g. study procedures, concomitant medications (only the subjects randomized to ARM-2 or 3).

Deviation from the inclusion/exclusion criteria

- · Deviation from the discontinuation criteria
- · Deviation from prohibited concomitant therapies
- · Subjects without follow-up data
- Subjects with the study drug compliance of <75%

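### Permitted steroid added after Week 24 counts as success in the primary analysis, and no planned sensitivity analysis or by-arm table would show whether a non-inferiority conclusion depends on it.

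*Protocol*

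**What the plan says.** **Steroid rules.** Protocol 6.2.1, on allowed therapies, permits oral and suppository steroid up to 10 mg/day prednisolone equivalent, with the proviso that "the dosages of corticosteroid oral drug and suppository should in principle remain unchanged from Week 24 to 48". It also allows joint injections except in the 28 days before an efficacy assessment, temporary intravenous steroid, and temporary steroid for conditions other than RA.

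**Consequences for the subject.** The withdrawal criteria in Protocol 5.3 do not name a steroid increase or an injection. The non-responder rule (Protocol 9.6, SAP 2.4) applies only when data are missing.

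**Analysis sets.** The primary analysis uses the mFAS, with the PPS as supplementary. SAP 3.1.2 introduces the PPS exclusions as significant deviations, with concomitant medications among the examples. The matching listed item is "Deviation from prohibited concomitant therapies". Steroids are not in the prohibited section, Protocol 6.2.2.

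**Sensitivity analyses and tables.** SAP 6.1 plans a generalized linear mixed model, an analysis using End of Study data for a missing final visit, and a logistic model without a steroid term. SAP 4.4 tabulates MTX exposure only.

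**Data.** Protocol 6.2 states: "The dosage and administration route of drugs used for treatment of RA during the study should be recorded in EDC".

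**The concern.** The randomised period is open label (Protocol 4.3.2). SDAI includes tender and swollen joint counts and two VAS scores (Protocol 7.2.4), which steroid can lower. If reduced MTX leaves some ARM-3 subjects undertreated, the investigator cannot raise MTX without withdrawing the subject (Protocol 5.3). Steroid within the limits of 6.2.1 remains open. More added steroid in ARM-3 than in ARM-2 is therefore plausible, though not shown.

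Such an imbalance would narrow the difference in remission rates and make non-inferiority easier to declare. Permitted use passes through both the mFAS and the PPS. No planned output would tell the reader whether it happened, in which direction, or whether the conclusion depends on it.

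**Working it through.** **Inputs from the documents**
- Interval: "The analysis on non-inferiority will be performed with a two-tailed confidence interval of 90" percent (Protocol 9.3), so one-sided 5% and z = 1.645.
- Margin: 15 percentage points, for ARM-3 minus ARM-2 (Protocol 9.2.1.1).
- Planning rates: "Assuming that the SDAI remission rate is 30% for both ARM-2 and ARM-3" (Protocol 9.4.1).
- Size: 110 per arm, allocated 1:1 (Protocol 9.4 and 9.4.1).

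**Input not in the documents**
- The frequency of added steroid after Week 24 and its effect on remission. Every shift below is an assumption.

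**The plan's own figure.** Power at 30% v 30% with 110 per arm:
- SE = √[(0.21 + 0.21)/110] = 0.0618.
- Power = Φ(0.15/0.0618 − 1.645) = 78.3%. Exact binomial enumeration of the Wald rule gives 78.8%.
- This is within 2 points of the stated 80%. Solving for 80% with the same formula gives 116 per arm, which does not bear on this point.

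**Method for the steroid question.** Take true rates at the margin, ARM-2 30% and ARM-3 15%. Add assumed gains from steroid. Then sum the binomial probabilities of all outcomes in which

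d − 1.645 × √[p2(1 − p2)/110 + p3(1 − p3)/110] > −0.15,

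where p2 and p3 are the observed rates and d = p3 − p2. The calculation is unstratified, because the documents give no country sizes.

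| Assumed gain, ARM-2 / ARM-3 (points) | Rates after gain | Non-inferiority declared |
|---|---|---|
| 0 / 0 | 30% v 15% | 5.2% |
| 3 / 3 | 33% v 18% | 5.1% |
| 5 / 5 | 35% v 20% | 5.1% |
| 5 / 3 | 35% v 18% | 2.4% |
| 2.5 / 5 | 32.5% v 20% | 11.3% |
| 0 / 3 | 30% v 18% | 13.5% |
| 0 / 5 | 30% v 20% | 22.1% |

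Hand check of the last row: SE = √[(0.21 + 0.16)/110] = 0.0580, and Φ((0.15 − 0.10)/0.0580 − 1.645) = Φ(−0.783) = 21.7%, close to the exact 22.1%.

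In subjects, 3 points is 0.03 × 110 = 3.3 and 5 points is 0.05 × 110 = 5.5.

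**Equal share of failures converted.** ARM-3 then gains slightly more, because it has more failures to convert.
- 5% converted: ARM-2 0.30 + 0.70 × 0.05 = 33.5%; ARM-3 0.15 + 0.85 × 0.05 = 19.25%; error 6.6%.
- 10% converted: 37% v 23.5%; error 8.2%.

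**Power of the proposed supplementary analysis**, same enumeration, true rates 30% v 30% before reclassification:
- 5% to 15% of remitters reclassified equally in both arms: 79.7% to 82.1%.
- 5% in ARM-2 and 10% in ARM-3 (28.5% v 27%): 72.7%.
- 5% in ARM-2 and 15% in ARM-3 (28.5% v 25.5%): 64.5%.

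**The case against.** **The PPS may already deal with it.** A reader might infer that no analysis set can touch steroid use, so that every subject with raised steroid is a remitter in both mFAS and PPS. The documents do not support that. The SAP 3.1.2 lead-in names concomitant medications without limiting them to prohibited ones, and SAP 2.3 provides a data handling meeting before lock with arm information removed. A breach such as an injection inside the 28 days could be excluded there. What remains is that the SAP does not say how a 6.2.1 breach is classed, that permitted use stays in, and that the PPS is only supplementary.

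**The rules are the same in both arms.** This stands. Equal point gains leave the error near 5%, and an imbalance towards ARM-2 lowers it. A reader might infer that the trial is biased towards non-inferiority, but the documents give no steroid data and so do not show it.

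**The route is limited.** Definitive RA exacerbation and a need for more MTX both lead to withdrawal, and a missing Week 48 result then counts as non-response. Oral and suppository dose is capped. This narrows the route but does not cover milder flares treated with permitted steroid.

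**The target of estimation matters.** If Week 48 remission is meant to be compared with permitted background therapy included, 30% v 18% is a true 12-point difference, inside the margin. The error rates above take remission without added steroid as the truth. That is a fair reason to keep the primary analysis and make the new one supplementary.

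**Hydroxychloroquine.** A reader might extend the point to it. Its dose condition sits in Protocol 6.2.2, the prohibited section, so a change may already fall under "Deviation from prohibited concomitant therapies". It is left out here.

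**Conclusion.** The gap is real but modest. Permitted steroid added after Week 24 counts as success if the subject is in remission at Week 48. The SAP does not say whether a breach of 6.2.1 removes a subject from the PPS, and no planned analysis or table shows steroid use by arm.

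The consequence depends on imbalance. Across the assumed point gains, false non-inferiority runs from 2.4% (ARM-2-heavy) through about 5% (equal) to 22.1% (5 points in ARM-3 only), against 5.2% with no shift. These figures rest on 110 per arm, true rates of 30% v 15%, an unstratified Wald interval, and assumed gains. They do not show that the trial is biased. They show that an imbalance of about three to six ARM-3 subjects would matter and would go unseen. This is a low-cost improvement and not a flaw in the primary analysis.

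**What to change.** Leave the treatment rules and the primary analysis unchanged.

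1. In SAP 6.1, add a supplementary analysis of the primary endpoint. It counts as non-remitters at Week 48 those subjects who, after randomisation, had new or increased systemic corticosteroid for RA, or a joint injection. It does not count a change of route at unchanged dose, or steroid for other indications.
2. Tabulate such use by arm for the period after randomisation.
3. In SAP 3.1.2, state whether a breach of Protocol 6.2.1 is a PPS deviation.

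Protocol 6.2 already requires dose and route of RA drugs in EDC, so the cost is SAP wording, one analysis and one table. The downside is a possibly lower remission rate and, if reclassification is unequal, lower power in that analysis (72.7% in the 5% v 10% case above). An injection soon after Week 24 would also count as failure, which is a strict reading and a further reason to keep the analysis supplementary.

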## 6.2.2 Prohibited concomitant therapy

DMARDs other than MTX and ADA are prohibited during the study. Concomitant use of Hydroxychloroquine in South Korea and Taiwan is acceptable, on condition that in principle the dosage should not change between Week 24 and 48. Subjects receiving a non-ADA bDMARD or JAK inhibitor will be withdrawn from the study immediately upon the start of such treatment.

Concomitant use of opioid analgesics except for Tramadol is prohibited in this study. Although the use of Tramadol is possible, when used it should be administered except for 3 days prior to the efficacy assessment.

#### 6.3 Compliance

Principal investigator/sub-investigator shall verify with each subject at each visit the status of dose (self-administration) concerning MTX, folic acid, and ADA to ensure their dose compliance. The patient compliance instruction should be provided at any time upon finding non-compliance to the instruction on dose (self-administration) given by the doctor. The data on dose compliance concerning study drugs to be recorded in EDC must be based on the record of actual dose (self-administration).

#### 7 Assessments

#### 7.1 Demography

The following information should be collected and recorded in EDC at Screening (within 8 weeks before the start of study treatment). In addition to the information, subject ID, the status of informed consent, and the results of eligibility assessment should also be recorded in EDC.

1) Gender

- 2) Age (at consent)
- 3) Race
- 4) Height and body weight
- 5) Time of RA diagnosis
- 6) Compliance to 1987 ACR revised criteria or 2010 ACR/EULAR criteria
- 7) RA treatment history (steroid, DMARDs, NSAIDs, etc.)
- 8) History of RA surgery
- 9) Medical history/Complication
- 10) Smoking history
- 11) 12-lead ECG (Not required if performed within 12 weeks before consent)
- 12) Infection disease test (Not required if performed within 2 years before consent):
  - Either skin tuberculin test or interferon gamma release assay (IGRA)
  - HBs antigen, HBs antibody, HBc antibody, and anti-HCV antibody

When a HBs Antigen (Ag)-negative subject is HBs Antibody (Ab) positive and/or HBc Ab positive, the subject must be tested for HBV-DNA quantification for at least once every 6 months.

#### 7.2 Efficacy assessments

#### 7.2.1 X rays of hands and feet

In accordance with the assessment schedule presented in the following table, X rays of subjects' hands and feet will be performed at screening, and Weeks 24 and 48 (or at early termination). The X-rays of the hands and feet are unnecessary to be performed for early termination if early termination occurs within 28 days after the last X-rays. The X-ray image of the hands and feet should be sent to the study secretariat along with the subject ID. The X-ray image of the hands and feet will be independently reviewed by the X-ray Imaging Review Committee to evaluate bone erosions in the regions specified on the left side of the figure shown below, and also to evaluate joint space narrowing in the results will be sent to the data center.

Bone erosions will be evaluated for each region in accordance with the following score:

Score 1: Small bone erosion

Score 2: Large bone erosion (Not extend over the imaginary middle of the bone)

Score 3: Large bone erosion (Extends over the imaginary middle of the bone)

Score 5: Complete collapse of the joint

The score will be 0 to 5 for each hand region, and 0 to 10 for each foot region. The maximum total erosion score of both hands will be 160 points, and that of both feet will be 120 points.

Joint space narrowing will be evaluated for each region in accordance with the following score:

Score 1: Localized or merely suspected

Score 2: Generalized narrowing (≥50% joint space remaining)

Score 3: Generalized narrowing (≤50% joint space remaining) or subluxation

Score 4: Disappearance of joint space, or anchylosis or luxation

The maximum total joint space narrowing score of both hands will be 120 points, and that of both feet will be 48 points.

Source: Swinkels HL, et al. 2001: 176-90

## 7.2.2 Tender joint count, swollen joint count, VAS (physician- and patientreported), and HAQ

In accordance with the assessment schedule presented in the following table, tender joint count, swollen joint count, VAS (physician- and patient-reported disease activities, and patient-reported pain score), and HAQ will be evaluated, and the results will be recorded in EDC.

HAQ score  $\leq 0.5$  is defined as functional remission.

## 7.2.3 CRP, ESR, MMP-3, RF, and anti-CCP antibody

In accordance with the assessment schedule presented in the following table, blood samples for CRP, ESR, MMP-3, RF, and anti-CCP antibody will be collected and evaluated. In South Korea and Taiwan, MMP-3 will be measured at the external laboratory only at the essential time points (blood collection at screening will be performed at Week 0 together with other assessments measured at the external laboratory). The results of measurement will be recorded in EDC.

## 7.2.4 SDAI

SDAI will be calculated with the following formula and based on the evaluation results of tender joint count, swollen joint count, VAS (physician- and patient-reported; 10 cm scale), and CRP.

• Tender joint count (28 joints) + Swollen joint count (28 joints) + Patient-reported disease activity / 10 + Physician-reported disease activity / 10 + CRP

Disease activities will be categorized to High disease activity: >26, Moderate disease activity: >11 to  $\leq$ 26, Low disease activity:  $\leq$ 11, and Remission:  $\leq$ 3.3.

## 7.2.5 CDAI

CDAI will be calculated with the following formula and based on the evaluation results of tender joint count, swollen joint count, and VAS (physician- and patient-reported; 10 cm scale).

• Tender joint count (28 joints) + Swollen joint count (28 joints) + Patient-reported disease activity / 10 + Physician-reported disease activity / 10

Disease activities will be categorized to High disease activity: >22, Moderate disease activity: >10 to  $\leq$ 22, Low disease activity:  $\leq$ 10, and Remission:  $\leq$ 2.8.

## 7.2.6 ACR 20, 50, 70 response rates, and ACR-N

ACR 20 response is defined as a subject meeting all of the following 3 criteria based on the evaluation results of tender joint count, swollen joint count, VAS (physician- and patient-reported), HAQ, and CRP. Also, the proportion of ACR 20 response will be referred to as ACR 20 response rate.

- ≥20% improvement in the tender joint count (of the total 68 joints) compared to Week 0 of treatment
- ≥20% improvement in the swollen joint count (of the total 66 joints) compared to Week 0 of treatment
- ≥20% improvement in ≥3 of 5 parameters (physician- and patient-reported disease activities, patient-reported pain score, HAQ, and CRP) compared to Week 0 of treatment

ACR 50 response, ACR 50 response rate, ACR 70 response, and ACR 70 response rate are defined by the standards that 20% improvement of ACR 20 response and ACR 20 response rate is replaced to 50% and 70% improvement, respectively.

Also, ACR-N will be the lowest improvement rate among the following 3 parameters:

- Improvement rate of the tender joint count (of the total 68 joints) compared to Week 0 of treatment
- Improvement rate of the swollen joint count (of the total 66 joints) compared to Week 0 of treatment
- The 3rd highest improvement rate among the 5 parameters (physician- and patient-reported disease activities, patient-reported pain score, HAQ, and CRP) compared to Week 0 of treatment

